10.4.2 Annual Reporting to the site IRB

The following items will be reported to the site IRB in summary at the time of Continuing Review:

- Serious and non-serious unanticipated problems
- SAEs that are possibly, probably, or definitely related to the research
- SAEs that are not related to the research
- All AEs.
- Serious and Non-Serious Protocol deviations
- Serious, continuing, and minor non-compliance
- Any trend or event that, in the opinion of the Investigator, should be reported

10.4.3 Investigator Reporting Responsibilities to the Sponsor

Adverse Events: Line listings, frequency tables, and other summary AE data will be submitted to the IND Sponsor when needed for periodic safety assessments, review of IND annual reports, review of IND safety reports, and in the preparation of final study reports.

SAEs (whether or not they are also UPs) must be reported on the Safety Expedited Report Form (SERF) and sent to the Sponsor Clinical Safety Office (CSO) by fax or e-mail attachment.

Deaths and immediately life threatening SAEs must be reported within one business day after the site becomes aware of the event. All other SAEs must be reported within three business days of site awareness.

SPONSOR CLINICAL SAFETY OFFICE CONTACT INFORMATION:

SAB Biotherapeutics, Inc.
ATTN: Clinical Safety Office
[name]
[name]

[contact]
[contact]
E-mail: [contact]

Non-Serious AEs that are UPs must also be reported on the SERF and sent to the CSO by fax or e-mail attachment no later than seven calendar days of site awareness of the event. The UPs that are not AEs are not reported to the Sponsor CSO.

Pregnancy: Although pregnancy itself is not an AE, events that meet SAE criteria during pregnancy, delivery, or in the neonate (e.g., congenital anomaly/birth defect) are reportable on the SERF. Pregnancy and pregnancy outcome data (e.g. delivery outcome, spontaneous or elective termination of the pregnancy) will be reported to the CSO within three business days of the site's awareness via email or fax.

10.5 FOLLOW-UP OF ADVERSE EVENTS AND SERIOUS ADVERSE EVENTS

AEs that occur following enrollment of the subject (by signing the informed consent) are followed until the final outcome is known or until the end of the study follow-up period.

SAEs that have not resolved by the end of the follow-up period are followed until the final outcome is known. If it is not possible to obtain the final outcome for an SAE (e.g. the subject is lost to follow-up), the reason that a final outcome could not be obtained will be recorded by the Investigator on the AE case report form (CRF), if the CRF is still open, and the SERF as applicable.

SAEs that occur after the study follow-up period that are reported to the Investigator and are assessed to be possibly, probably, or definitely related to the study agent must be reported to the CSO, as described above.

10.6 Sponsor's Reporting Responsibilities

Serious, unexpected, suspected adverse reactions (SUSARs) as defined in 21 CFR 312.32 will be reported to FDA and all participating Investigators as IND Safety Reports. The sponsor will also submit a brief report of the progress of the investigation to the FDA on an annual basis as defined in 21 CFR 312.33.

11 CLINICAL MONITORING STRUCTURE

11.1 Site Monitoring Plan

As per ICH-GCP 5.18 and FDA 21 CFR 312.50, clinical protocols are required to be adequately monitored by the study sponsor. Study monitoring will be conducted according to the “NIAID Intramural Clinical Monitoring Guidelines” or similar guideline currently in use. Monitors under contract to SAB or CRO will visit the clinical research site to monitor aspects of the study in accordance with the appropriate regulations and the approved protocol. The objectives of a monitoring visit will be:

- 1) To verify the existence of signed informed consent documents and documentation of the ICF process for each monitored subject;
- 2) To verify the prompt and accurate recording of all monitored data points and prompt reporting of all SAEs;
- 3) To compare Medidata Rave data abstracts with individual subject records and source documents (subject charts, laboratory analyses and test results, physicians' progress notes, nurses' notes, and any other relevant original subject information);
- 4) To help ensure Investigators are in compliance with the protocol. The monitors also will inspect the clinical site regulatory files to ensure that regulatory requirements (Office for Human Research Protections-OHRP), FDA, and applicable guidelines (ICH-GCP) are being followed. During the monitoring visits, the Investigator (and/or designee) and other study personnel will be available to discuss the study progress and findings of the monitoring visit.

A specific protocol monitoring plan will be discussed with the PI and study staff prior to enrollment. The plan will outline the frequency of monitoring visits based on such factors as study enrollment, data collection status and regulatory obligations.

11.2 Data and Safety Monitoring

11.2.1 Investigator Safety Monitoring

The Investigator or designee may interrupt the administration of study drug to an individual subject, or enrollment into this study if indicated for unanticipated problems or AEs. In addition, the Investigators are responsible for:

- Protecting the safety and welfare of subjects
- Evaluating subject safety, including physician assessment of AEs for seriousness, severity, and causality
- Notifying the sponsor of SAEs and immediately-reportable events
- Providing detailed written reports, including confirmatory tests promptly following immediate initial reports
- Informing the IRB of SAEs

11.3 Safety Review and Communications Plan (SRCP)

A Safety Review and Communication Plan (SRCP) has been developed for the protocol. The SRCP is an internal communications document between the PI and the IND Sponsor Clinical Safety Office (CSO), which delineates the safety oversight responsibilities of the PI, the CSO, and other stakeholders. The SRCP also includes the overall plan for conducting periodic safety surveillance assessments.

11.4 Safety Monitoring Plan

PPD has established through their Safety Monitoring Plan a process that defines a committee charged with reviewing the accumulating data as the trial progresses to monitor safety, effectiveness and trial conduct. The Safety Monitoring Plan will be developed by a safety specialist from PPD's pharmacovigilance group. This plan then would be reviewed by the principle investigator, a medical monitor from PPD, as well as medical monitors and subject matter experts (e.g. pharmacokinetic, biostatistics, etc.) identified by the sponsor. While the committee could have up to ten members, including project and study managers, there will be a core committee designated of at least four members that are charged with authorizing study advancement. The plan will be included in the Trial Master File at the end of the study.

11.5 Sponsor Medical Monitor

A Medical Monitor representing the IND Sponsor will be appointed for oversight of safety in this clinical study. The Sponsor Medical Monitor will be responsible for performing safety assessments as outlined in a Safety Review and Communications Plan (SRCP).

11.6 Treatment Interruption or Discontinuation

A subject's study drug infusion may be discontinued at any time at the subject's request or at the discretion of the Investigator or the Sponsor. The following may be justifiable reasons for the Investigator to discontinue a subject from SAB-176 infusion:

- The subject was erroneously included in the study (i.e., was found to not have met the eligibility criteria)
- The subject experiences an intolerable AE
- The subject is unable to comply with the requirements of the protocol

- The subject participates in another investigational study without the prior written authorization of the Sponsor

The criteria for slowing or stopping a given infusion is discussed in Section 5.3

11.7 Pausing Rules

If any of the following criteria are met at any time the study will be paused to further enrollment until assessed by the sponsor medical monitor:

- Any SAE as defined in Section 10.3 that can be possibly, probably, or definitively attributed to the study drug
- Three or more subjects in the same cohort experiencing the same Grade 2 or higher adverse effect that can be possibly, probably, or definitively attributed to the study drug
- Two or more subjects develop the same or clinically similar Grade 3 AE or laboratory abnormality
- Two or more subjects develop a serum creatinine \geq Grade 2 toxicity (≥ 1.8 mg/dL)
- Two or more subjects develop \geq 1.5-fold increase in serum creatinine level from baseline
- Two or more subjects develop GFR <70 mL/min, irrespective if serum creatinine is normal range or Grade 1
- Two or more subjects develop a serum creatinine \geq Grade 2 toxicity in PT and/or PTT (i.e. one grade 2 PT and one grade 2 PTT would meet this pausing rule)

The sponsor medical monitor can request information needed (such as a listing of graded AEs) and unblinded randomization scheme (directly from the site investigational pharmacy group) to evaluate the data. For individual subject unblinding, the site will follow their unblinding procedures per SOP-AUSCLN-506. The sponsor medical monitor will ultimately make the decision to either resume the study or stop the study.

If the trial is stopped due to unacceptable adverse events or stopping criteria, the IRB will be notified.

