3.2 Study Design

This safety and tolerability study of intravenous (IV) SAB-176 consists of up to 4 single dose-levels or cohorts (cohort 1–4) in a double-blind, randomized, placebo-controlled dose-escalating cohort design. Four cohorts of 2–10 subjects each will be administered a single IV dose of SAB-176 or saline placebo. At very low doses, the concern is primarily allergic or T-cell activation/cytokine storm, so small cohort sizes should be utilized. As the target dose is approached, the sample size will increase to increase the likelihood of detecting toxicity events. The cohorts and dose levels are outlined in [Table 1](#).

Table 1: Cohorts and Dose Levels

Cohort	Number of Subjects Receiving SAB-176				Number of Subjects Receiving Saline Control
	1 mg/kg	10 mg/kg	25 mg/kg	50 mg/kg	
1	2				1
2		4			2
3			6		2
4				8	2

The number of subjects dosed will follow the limitations below:

- The first three subjects of each cohort will be dosed every other day (48-hour interval).
- For Cohorts 2–4, 48 hours after the third subject is dosed, up to 3 subjects may be dosed per day, until the cohort is completed, and no more than 8 subjects will be dosed per week.
- For cohorts 2, 3, and 4, additional dosing in the cohort may continue only after the safety committee recommends continuation after reviewing the safety data from the 3 initial subjects of the cohort.
- After the first three in each cohort, subsequent subjects will be observed for at least 4 hours before beginning the next infusion in the next subject.

Table 2. Example of dosing timeline

	Infusion Day								
	1	2	3	4	5	6	7	8	9
Subject 1	X								
Subject 2			X						
Subject 3					X				
Subject 4							X*		

Table 2. Example of dosing timeline (con't)

	Infusion Day								
	1	2	3	4	5	6	7	8	9
Subject 5							X (≥4 hrs post Subject 4)		
Subject 6							X (≥4 hrs post Subject 5)		
Subject 7								X	
Subject 8								X (≥4 hrs post Subject 7)	
Subject 9								X (≥4 hrs post Subject 8)	
Subject 10									X

* Additional enrollment in the cohort may continue only after the safety committee recommends continuation after reviewing the safety data from the three initial subjects of the cohort.

NOTE: Only 1 subject should be infused at any given time. An infused subject should be observed for at least four hours prior to beginning the next infusion.

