3.3 Definitions for the Purpose of this Study

Definitions for the Purpose of this Study:

Enrolled

For the purpose of collecting data and samples and reporting adverse events (AEs), a subject will be considered enrolled beginning from when the informed consent form is signed until the subject is considered “screen failure”, “discontinued”, or “completed”.

Randomized

Subjects are considered randomized when they meet all of the following criteria:

- Enrolled (as defined above)
- Confirmation that the inclusion and exclusion criteria are met
- Randomization number is assigned

Screen Failures

Subjects are considered screen failures when they meet one or more of the following criteria after signing consent:

- Screening tests reveal that the subject is ineligible
- Subject withdraws consent before being randomized

Discontinued

Subjects are considered discontinued when they meet one or more of the following criteria:

- Subject withdraws consent after being randomized and prior to the completion of Day 90 (see Section 4.6)
- Subject is withdrawn after enrollment by Investigator (see Section 4.7) including lost to follow-up

Completed

Subjects are considered completed when they are followed through Study Day 90 and complete the final study follow-up visit (Study Day 90).

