4.8 Discontinuation of Study

SAB Biotherapeutics as the study sponsor, the study site IRB, and the Food and Drug Administration (FDA) may terminate this study at any time. Reasons for terminating the study may include, but are not limited to, the following:

- The incidence or severity of an AE in this or other studies indicates a potential health hazard to subjects.
- If there is one death, irrespective of attribution by the investigator/medical monitor. Subject enrollment is unsatisfactory.
- Data recording is inaccurate or incomplete.
- Investigators do not adhere to the protocol or applicable regulatory guidelines in conducting the study.

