10.1.1 Causality

Causality (likelihood that the event is related to the study agent) will be assessed considering the factors listed under the following categories:

Definitely Related:

- Reasonable temporal relationship
- Follows a known response pattern
- Clear evidence to suggest a causal relationship
- There is no alternative etiology

Probably Related:

- Reasonable temporal relationship
- Follows a suspected response pattern (based on similar agents)
- No evidence of a more likely alternative etiology

Possibly Related:

- Reasonable temporal relationship
- Little evidence for a more likely alternative etiology

Unlikely Related:

- Does not have a reasonable temporal relationship
OR
- Good evidence for a more likely alternative etiology

Not Related:

- Does not have a temporal relationship
OR
- Definitely due to an alternative etiology

Note: Causality assessment is based on available information at the time of the assessment of the AE. The Investigator may revise the causality assessment as additional information becomes available.

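### The mandatory pausing rule in Section 11.7 has no death criterion, so a single death judged unlikely or not related causes no automatic pause

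*Protocol*

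**What the plan says.** Section 11.7 is the automatic safety brake. If any of its seven criteria is met, "the study will be paused to further enrollment until assessed by the sponsor medical monitor". The one criterion that a single subject can meet is "Any SAE as defined in Section 10.3 that can be possibly, probably, or definitively attributed to the study drug". The others count two or more subjects, or three for the same Grade 2 or higher effect within a cohort.

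Section 4.8 lists reasons for which the sponsor, the site IRB or FDA may terminate the study. One of them is "If there is one death, irrespective of attribution by the investigator/medical monitor".

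Under Section 10.1.1 an event is unlikely related if it lacks a reasonable temporal relationship, or if there is "Good evidence for a more likely alternative etiology". Sections 5.1 and 10.2 together mean that this judgment is made by an investigator who is blinded to treatment.

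On notification, Section 10.4.3 makes no distinction by attribution: "Deaths and immediately life threatening SAEs must be reported within one business day after the site becomes aware of the event".

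**The concern.** The authors decided in 4.8 that attribution should not filter a death. The rule that operates without anyone having to decide, 11.7, does filter it. Attribution is not a general condition of 11.7 either, since most of its criteria do not mention it. For example, this one pauses the study with no causality judgment at all: "Two or more subjects develop GFR <70 mL/min, irrespective if serum creatinine is normal range or Grade 1".

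At stake is the default while a death is being assessed. If an 11.7 criterion is met, enrollment stops, and the sponsor medical monitor can obtain the unblinded randomization scheme and decides whether to resume or stop. If none is met, dosing in an open cohort goes on until someone chooses to intervene. Section 8.1.1 describes the risks of the product as largely unknown, so a blinded opinion on causality is a weak basis for switching off that default.

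**Working it through.** No arithmetic beyond counting applies. The test case is one death, judged unlikely or not related, with no other event in the study. Each criterion of 11.7 in turn:

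1. SAE possibly, probably or definitively attributed to study drug: one subject is enough, but attribution fails. Not met.
2. Same Grade 2 or higher effect in three or more subjects of one cohort, attributed: needs three subjects and attribution. Not met.
3. Same or clinically similar Grade 3 event or laboratory abnormality: needs two subjects. Not met.
4. Creatinine of Grade 2 or higher: needs two subjects. Not met.
5. Creatinine at least 1.5 times baseline: needs two subjects. Not met.
6. GFR below 70 mL/min: needs two subjects. Not met.
7. Grade 2 PT and/or PTT: needs two subjects. Not met.

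Result: 0 of 7 met. One criterion can be met by a single subject (no. 1) and 7 − 1 = 6 cannot. Two carry attribution wording (nos. 1 and 2) and 7 − 2 = 5 do not. The only criterion that one death could meet is thus one of the two that depend on attribution.

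The same case under the neighbouring sections:

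- **11.8:** the SAE criterion has the same attribution condition and there is no death criterion. The death alone would bar escalation only if it were an immediate hypersensitivity or cytokine storm event, which would hardly be judged unrelated.
- **4.8:** the death is listed, but as a reason for which the study may be terminated. Nothing follows automatically.
- **10.4.3:** the sponsor must be told within one business day. This is a reporting duty, not a pause.
- **10.4.1, 10.4.2 and 10.6:** seven-day IRB reporting covers related SAEs, serious protocol deviations and unanticipated problems, and an unanticipated problem also requires relatedness under 10.3. Unrelated SAEs go to the IRB in summary at Continuing Review. The expedited FDA reports are for suspected reactions. Section 11.2.1 asks the investigator to inform the IRB of SAEs but sets no deadline. Of the three bodies named in 4.8, only the sponsor is therefore assured prompt notice of such a death.
- **11.2.1:** the investigator may interrupt enrollment. This is discretionary.

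The case can coincide with active dosing. Subjects are followed to Day 90, while 11.8 allows the next cohort to be considered once Day 7 results of the last subject are in. A death in an earlier cohort can therefore occur while a later cohort is being infused.

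**The case against.** The strongest counter-argument is that 11.7 is coherent as it stands. A single event needs attribution, while the five criteria without attribution need recurrence, and recurrence stands in for a causality judgment. Two renal signals suggest a shared drug effect; one death with good evidence of another cause does not. The uncovered case is also the one where a pause adds least. The possibly related category needs only a reasonable temporal relationship and little evidence for a more likely cause, so an unexplained death soon after infusion already triggers 11.7. If causality is later revised upward, as 10.1.1 allows, 11.7 applies from then on. The sponsor knows within one business day and may halt, the investigator may interrupt, and a core committee authorizes advancement (11.4). The Safety Review and Communications Plan (11.3) and the Safety Monitoring Plan (11.4) are not shown and could prescribe a response to a death.

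Most of this stands, and it makes the gap small. It does not close it, because every backstop in the protocol depends on someone choosing to act.

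A reader might infer three stronger points that the protocol does not support.

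- **That 4.8 and 11.7 contradict each other.** Section 4.8 grants a power to terminate; 11.7 sets a mandatory pause. Both can be followed at once, and nothing requires each discretionary ground for termination to be an automatic pause as well.
- **That an 11.7 pause leaves consented subjects open to infusion**, because it refers to further enrollment and Section 3.3 says "a subject will be considered enrolled beginning from when the informed consent form is signed". That definition is expressly limited to collecting data and samples and reporting adverse events. The protocol also uses the word for dosing: the design text in 3.2 says "additional dosing in the cohort may continue only after the safety committee recommends continuation after reviewing the safety data from the 3 initial subjects", and the Table 2 footnote states the same condition with enrollment in place of dosing. Section 11.7 most plausibly already stops infusions.
- **That 15 of 27 subjects are exposed by the gap**, from (6 − 3) + (8 − 3) + (10 − 3) = 3 + 5 + 7 = 15. That counts everyone dosed after the three-subject reviews in Cohorts 2 to 4. Only subjects infused between such a death and a decision to stop would be affected. At the Table 2 pace of up to three a day, dosing after those reviews takes about 1, 2 and 3 days in the three cohorts, so the windows can be short, though slower dosing would lengthen them.

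**Conclusion.** The point holds as a narrow gap. A single death judged unlikely or not related meets none of the seven criteria in 11.7, so no default stop applies while it is assessed. What escapes is a death remote from infusion, or one with apparently good evidence of another cause. This is a minor, optional improvement. It does not touch the sample size or any analysis.

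The conclusion rests on the protocol text alone and would fall away in practice if one of the two safety plans already holds dosing after any death. The protocol gives no death rate. The event is assumed to be very rare in healthy volunteers, and no frequency is estimated.

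**What to change.** Add one criterion to 11.7: any death, irrespective of attribution, with dosing held until the sponsor medical monitor has assessed it. Leave 11.8 unchanged. A clearly unrelated death should not label a dose level as unsafe, and the 11.7 pause followed by the medical monitor's decision to resume or stop is enough.

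The cost is one bullet with its clause on dosing, and possibly a short pause for a death that proves clearly unrelated, such as an accident.

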- Other adverse reactions not specified, that are concerning for infusion related adverse events

After clinical assessment, and resolution or improvement of the event of concern, the infusion may be resumed. If the event is not resolving in a reasonable amount of time, the infusion will not be resumed.

However, in order to establish absolute criteria for stopping an infusion – the treatment should be immediately stopped should any of the following occur:

- Profound hypotension (systolic blood pressure < 85 mmHg)
- Shortness of breath, wheezing, or sustained (i.e., ≥ 10 seconds) oxygen saturation < 92% on room air
- Severe (Grade ≥ 3) local infusion site reactions, including pain, tenderness, erythema, or swelling as defined in the protocol-specified toxicity grading scale
- Body core temperature exceeding 38.5°C
- Suspected sepsis
- Severe chest pain
- Suspected anaphylaxis

The subject's actual time of drug administration will be recorded in the source documents.

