11.8 Dose Escalation Rules

When the results from the Day 7 visit for the last subject in a cohort (e.g., Cohort 1) are available safety parameters will be analyzed to determine the overall safety of that dose-level (e.g., 1 mg/kg). If any of the following criteria are met, the corresponding dose-level is not considered “acceptably safe”, and the study will not proceed to the next higher dose group (as the review is blinded, this will be across treatment arms).

- Any SAE that can be possibly, probably, or definitively attributed to the study drug
- Any immediate hypersensitivity or cytokine storm events
- Two or more subjects with asymptomatic positive anti-IgG (rheumatoid factor)
- One or more subjects with positive anti-IgG (rheumatoid factor) with associated rheumatologic symptoms (i.e. arthralgia, myalgia, etc.)
- Two or more subjects across all cohorts experience the same Grade 3 or higher adverse effect that can be possibly, probably, or definitively attributed to the study drug

- Three of the first 10 subjects (30%) experience the same grade 2 or higher adverse effect that can be possibly, probably, or definitively attributed to the study drug or any time thereafter 30% of enrolled subjects have the same grade 2 or higher 'related' AE.
- Two or more subjects across cohorts develop a serum creatinine \geq Grade 2 toxicity (≥ 1.8 mg/dL) or doubled from baseline (whichever is lower)

If any of the above criteria are met at any time, then the medical monitor will evaluate unblinded study data and make a determination about continuation of the study and/or amendment of the protocol.

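### No pausing or escalation criterion counts permanently stopped infusions, and in Cohort 1 the three-subject Grade 2 lines cannot be met by SAB-176 recipients alone

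*Protocol*

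**What the plan says.** **Stopping one infusion.** Section 5.3 lists absolute criteria under which "the treatment should be immediately stopped should any of the following occur". They include a core temperature above 38.5°C and a Grade 3 or worse infusion-site reaction. For lesser events, among them fever and chills, the infusion may be slowed or held: "If the event is not resolving in a reasonable amount of time, the infusion will not be resumed". Section 11.6 gives further grounds to discontinue, among them: "The subject experiences an intolerable AE".

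**Pausing the study.** The general Grade 2 line in 11.7 is "Three or more subjects in the same cohort experiencing the same Grade 2 or higher adverse effect", with the effect at least possibly attributed to study drug. A pause lasts until the sponsor medical monitor has assessed it. The monitor may request the unblinded scheme and decides whether to resume or stop.

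**Escalating.** The general Grade 2 line in 11.8 is "Three of the first 10 subjects (30%) experience the same grade 2 or higher adverse effect", again if related. A limb for 30% of enrolled subjects applies only after those first 10. The review is blinded and follows the last subject's Day 7 visit.

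**Cohort sizes and committee.** Table 1 in 3.2, under "Number of Subjects Receiving SAB-176", gives 2, 4, 6 and 8, with 1, 2, 2 and 2 on saline. On the committee: "For cohorts 2, 3, and 4, additional dosing in the cohort may continue only after the safety committee recommends continuation", after review of the first three subjects. Section 11.4 adds that "there will be a core committee designated of at least four members that are charged with authorizing study advancement".

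**The concern.** Tolerability at each dose level is part of the primary objective. An infusion ended for a related Grade 2 or higher AE is a tolerability failure, and it leaves that dose only partly tested. Yet 11.7 and 11.8 count graded effects and laboratory findings, never a stopped infusion, and their general lines need the same effect (in one case a clinically similar one) in several subjects.

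Two situations fall through. In Cohort 1, both recipients can fail to complete the lowest dose for one and the same effect without meeting a criterion. In any cohort, two infusions can be ended for different related effects without meeting a general line. In Cohorts 2–4, dosing can then go on once the three-subject review is past. At stake is whether the medical monitor must look at such cases, with access to the allocation, or may do so only if someone refers them.

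**Working it through.** **Inputs.** Cohort sizes are from Table 1 and thresholds from 11.7 and 11.8. The protocol gives no event rates, so every rate below is an assumption.

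**Plan's own figures.** Cohort totals are 2+1 = 3, 4+2 = 6, 6+2 = 8 and 8+2 = 10. Their sum is 27, as stated; cumulatively they are 3, 9, 17 and 27. The 11.8 threshold is 3/10 = 30%, as stated.

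**Criteria against the two cases.** Case A: both Cohort 1 recipients are stopped for the same related, non-serious Grade 2 effect, not classed as hypersensitivity or cytokine storm. Case B: two subjects in one cohort are stopped for unlike related, non-serious effects, for example a Grade 3 site reaction and a temperature above 38.5°C (taken as Grade 2 or 3).

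| Criterion | Case A | Case B |
|---|---|---|
| Related SAE (11.7, 11.8) | No, non-serious | No, non-serious |
| Same Grade 2+ effect, 3 in cohort (11.7) | No, 2 | No, 1 of each |
| Same or similar Grade 3, 2 subjects (11.7) | No, Grade 2 | No, unlike |
| Same Grade 3+ effect, 2 subjects (11.8) | No, Grade 2 | No, unlike |
| Same Grade 2+ effect, 3 of first 10, then 30% (11.8) | No, 2, and only 3 subjects dosed | No, 1 of each, if no other subject has either effect |
| Hypersensitivity or cytokine storm (11.8) | No, by definition of the case | Only if so classed |
| Creatinine, GFR, PT/PTT, rheumatoid factor | Only if separately abnormal | Only if separately abnormal |

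**Cohort 1, chance that the 11.7 line is met.** Let r be the rate of the same related Grade 2+ effect per recipient, stopped or not, and q the rate in the saline subject.

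- P(3 of 3) = r²q, which is at most q. With r = 0.5 and q = 0.05 it is 0.25 × 0.05 = 0.0125.
- Given that both recipients have the effect, the probability is q: 1/2/5% for assumed q = 1/2/5%.
- A line counting two stops is met with certainty in that case.

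**How often both recipients would be stopped.** At a stop rate p per recipient the probability is p²: 1/4/9/25% for assumed p = 10/20/30/50%.

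**Carry-forward.** Cohorts 1 and 2 total 9 subjects, so all lie within the first 10. After two cases in Cohort 1, the 11.8 line is met if at least one of the four Cohort 2 recipients has the same effect: 1 − (1 − p)⁴ = 34/59/76/94%, with the same assumed values now used as the effect rate. That comes only after dosing at 10 mg/kg has begun.

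**Subjects dosed after the in-cohort review.** 6 − 3 = 3, 8 − 3 = 5 and 10 − 3 = 7 in Cohorts 2, 3 and 4.

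**False pauses under the proposed line.** P(X ≥ 2), X binomial over all subjects in a cohort, saline included, at an assumed chance-stop rate:

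| Cohort (n) | 1% | 2% | 5% |
|---|---|---|---|
| 1 (3) | 0.030% | 0.118% | 0.725% |
| 2 (6) | 0.146% | 0.569% | 3.277% |
| 3 (8) | 0.269% | 1.034% | 5.724% |
| 4 (10) | 0.427% | 1.618% | 8.614% |
| Study, 1 − product of complements | 0.87% | 3.30% | 17.27% |

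**The case against.** The strongest reply is that in Cohort 1 a review is already compulsory. Once both recipients have been stopped, no active dose is left in the cohort, so a pause could spare at most the saline subject. Cohort 2 is held anyway until the Day 7 results are reviewed and the core committee authorises advancement. This stands. A reader might infer from the gap that the study could move to 10 mg/kg unreviewed; the protocol does not support that. The gain in Cohort 1 is a mandatory medical-monitor assessment with access to the unblinded scheme, not a new hold.

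Second, 3.2 says that the main low-dose concern is allergy or cytokine storm, and 11.8 blocks escalation after one such event. Anaphylaxis or allergic wheeze would fall there, and some other stops could be related SAEs as medically important events. This also stands and narrows Case A, chiefly to fever, chills or hypotension not given such a label. How those would be graded depends on the DAIDS table, which the protocol does not reproduce.

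Third, Cohorts 2–4 have the three-subject committee review, the investigator may interrupt enrolment at any time (11.2.1), and the Safety Monitoring Plan and SRCP may say more. The first two are real, but neither is a criterion tied to stops. The other two documents are not available, so the point covers 11.7 and 11.8 only.

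One could also read the 30% limb of 11.8 as running from the first subject, so that 2 of 3 would meet it. The wording places it after the first 10.

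**Conclusion.** The point holds as a gap in the binding criteria. It is not a gap in all oversight, and no stated figure is wrong. In Cohort 1, recipients alone cannot meet the 11.7 Grade 2 line, and the 11.8 line cannot be met before 10 mg/kg unless the saline subject has the same related effect. The response to two stops in two recipients then rests on blinded review and committee discretion. In any cohort, two unlike related, non-serious stops meet no general Grade 2 or 3 line. In Cohorts 2–4 this can leave up to 3, 5 or 7 subjects to be dosed after the last planned in-cohort review.

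Two stronger readings are not supported. One is that the tenfold step is itself unsafe: 5.4 puts 1 mg/kg about 47 times below the maximum recommended starting dose, so 10 mg/kg is also below it. The other is a large, quantified gain in detection for unlike stops in Cohorts 2–4. A plain binomial for two or more stops also counts stops for the same effect, which the present lines may catch, and the protocol gives no basis for conditioning on unlike effects. No such gain is claimed.

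The size rests on assumed rates and on reading the 11.7 pause on enrolment as covering dosing. The change is worth making because it is cheap; its priority lies between optional and recommended.

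**What to change.** Add one criterion to 11.7 only: *two or more subjects in the same cohort whose infusion is permanently stopped under Section 5.3 or 11.6 for a Grade 2 or higher AE judged at least possibly related to study drug, whether or not the effects are the same.*

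Count it on blinded data across both arms. An infusion that is slowed, or held and then completed, does not count, nor does a stop for a Grade 1 event. The existing pause and medical-monitor decision apply. Do not add it to 11.8: two stops should force an assessment, not by themselves rule that the dose level is not acceptably safe.

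The cost is one line of text, with no new procedure and no new route to unblinding. The downside is an occasional false pause until the monitor has assessed it, about 0.9/3.3/17% over the whole study at the assumed chance-stop rates of 1/2/5%, with no automatic block on escalation.
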